3.0 Patient Eligibility

3.1 Inclusion Criteria

3.11 Age \geq 18 years.

3.12 Confirmed acute index (original venous thrombotic) event: lower extremity or upper extremity (jugular, innominate, subclavian, axillary, brachial) DVT, PE, splanchnic (hepatic, portal, splenic, mesenteric, renal, gonadal), or cerebral vein thrombosis for which the patient has received \geq 180 days (but \leq 365 days) of anticoagulant therapy prior to registration. The date, imaging modality, and location of index event will be required. The date of initiation and specific type of anticoagulants used will also be required.

3.13 Active cancer defined as metastatic disease and/or any evidence of cancer on cross-sectional or PET imaging, cancer related surgery, chemotherapy or radiation therapy within the past 6 months. Note: non-melanoma skin cancer does not meet the cancer requirement.

3.14 Life expectancy \geq 6 months.

3.15 ECOG Performance Status (PS) of 0, 1, or 2. (Form is available on the ACCRU web site
[REDACTED]

3.16 The following laboratory values obtained \leq 30 days prior to registration.

- Hemoglobin \geq 8 g/dL
- Platelet count \geq 50,000/mm³
- Alanine aminotransferase (ALT) or Aspartate transaminase (AST) \leq 3 x ULN
- Calculated creatinine clearance must be \geq 30 ml/min using the Cockcroft-Gault formula below:

Cockcroft-Gault Equation:

$$\text{Creatinine clearance for males} = \frac{(140 - \text{age})(\text{weight in kg})}{(72)(\text{serum creatinine in mg/dL})}$$

$$\text{Creatinine clearance for females} = \frac{(140 - \text{age})(\text{weight in kg})}{(72)(\text{serum creatinine in mg/dL})} * (0.85)$$

3.17 Negative serum or urine pregnancy test done \leq 7 days prior to registration, for women of childbearing potential only.
 Note: A woman of childbearing potential (WOCBP) is defined as any female who has experienced menarche and who has not undergone surgical sterilization (hysterectomy or bilateral oophorectomy) and is not postmenopausal. Menopause is defined as 12 months of amenorrhea in a woman over age 45 years in the absence of other biological or physiological causes.

3.18 Ability to provide informed written consent.

3.19 Willing to undergo monthly follow-up assessment, either in person at the enrolling institution or by telephone (script in Appendix V).

3.2 Exclusion Criteria

3.21 Any of the following because this study involves an investigational agent whose genotoxic, mutagenic and teratogenic effects on the developing fetus and newborn are unknown:

- Pregnant women
- Nursing women
- Men or women of childbearing potential who are unwilling to employ adequate contraception
 - Note: Women of child bearing potential must agree to follow instructions for method(s) of contraception for the duration of treatment with study drug (s) plus 33 days after finishing the last dose.
 - Males who are sexually active with WOCBP must agree to follow instructions for method(s) of contraception for the duration of treatment with study drug (s) plus 93 days after finishing the last dose.
 - Azoospermic males and WOCBP who are continuously not heterosexually active are exempt from contraceptive requirements. However they must still undergo pregnancy testing as described in this section.

Note: Investigators shall counsel WOCBP and male subjects who are sexually active with WOCBP on the importance of pregnancy prevention and the implications of an unexpected pregnancy. Investigators shall advise WOCBP and male subjects who are sexually active with WOCBP on the use of highly effective methods of contraception. Highly effective methods of contraception have a failure rate of $< 1\%$ when used consistently and correctly.

At a minimum, subjects must agree to the use of one method of highly effective contraception as listed below:

HIGHLY EFFECTIVE METHODS OF CONTRACEPTION

- Male condoms with spermicide
- Hormonal methods of contraception including combined oral contraceptive pills, vaginal ring, injectables, implants and intrauterine devices (IUDs) such as Mirena® by WOCBP subject or male subject's WOCBP partner.
- Female partners of male subjects participating in the study may use hormone based contraceptives as one of the acceptable methods of contraception since they will not be receiving study drug
- IUDs, such as ParaGard®
- Tubal ligation
- Vasectomy.
- Complete Abstinence*

*Complete abstinence is defined as complete avoidance of heterosexual intercourse and is an acceptable form of contraception for all study drugs. Acceptable alternate methods of highly effective contraception must be discussed in the event that the subject chooses to forego complete abstinence

3.22 Active major bleeding.

3.23 Severe hypersensitivity reaction to apixaban (e.g., anaphylactic reactions).

3.24 Current use of strong CYP3A4 inducers or inhibitors (see list in appendix II).
NOTE: Patients may be eligible if they transition to an alternative agent (see section 8.1) or are able to stop CYP3A4 inducer or inhibitor.

3.25 Current use of thienopyridine therapy (clopidogrel, prasugrel, or ticagrelor) that will be continued on study.

3.26 Severe liver disease (known cirrhosis Childs Pugh class B or C), or active hepatitis.

3.27 Documented venous thromboembolism while on therapeutic anticoagulation (“anticoagulation failure”).

3.28 Mechanical heart valve.

3.28 Documented hemorrhagic tendencies (e.g., hemophilia).

3.29 Bacterial endocarditis.

3.30 Any of the following conditions:

- Intracranial bleeding \leq 6 months prior to randomization
- Intraocular bleeding \leq 6 months prior to randomization
- Gastrointestinal bleeding and/or endoscopically proven ulcer \leq 6 months prior to randomization
- Head trauma or major trauma \leq 1 month prior to randomization
- Neurosurgery \leq 2 weeks prior to randomization
- Major surgery \leq 1 week prior to randomization
- Gross hematuria at the time of randomization

4.0 Test Schedule

| Tests and procedures | ≤ 30 days prior to registration (baseline) | Every 30 days after the start of treatment (± 1 week) ³ | End of treatment |
|--|---|---|------------------|
| History and exam (including height and weight) | X | | |
| ECOG PS | X | X | |
| Adverse event assessment ³ | X | X | X |
| Hematology: 
 • CBC | X ¹ | | |
| Chemistry: 
 • SGOT (AST) or ALT • Creatinine | X ¹ | | |
| Selected concomitant meds ³ (see CRF for this form) | X | X | X |
| Pregnancy test ² | X | | |
| Patient education regarding signs and symptoms of thrombosis (Appendix VI) | X ⁵ | | |
| Patient Contact (including bleeding assessment, see App. IV and V) ³ | X | X | X |
| Patient compliance documentation ⁴ | | X | X |

1

1. ≤ 30 days prior to registration.
2. For women of childbearing potential only. Negative serum or urine pregnancy test done ≤ 7 days prior to registration.
3. If it is not feasible for the patient to return to the enrolling center for the monthly reassessment, a detailed history will be obtained by phone using a structured interview (see appendix V).
4. Use the questions in Appendix VII to obtain this information, and document the information on the appropriate case report form.
5. Prior to 1st study drug administration: Appendix VI given to patient and patient educated on signs/symptoms of potential thrombosis to monitor and report to study staff.

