7.0 Protocol Treatment

7.1 Treatment Schedule

| Agent | Dose Level | Frequency | Route |
|----------|------------|--------------------------------------|-------|
| Apixaban | 2.5 mg | Twice daily for 12 months (365 days) | Oral |
| Apixaban | 5 mg | Twice for daily 12 months (365 days) | Oral |

*If a dose of apixaban is not taken at the scheduled time, the dose should be taken as soon as possible (+/-4 hours of the normal scheduled dose) on the same day and the prescribed dosing schedule should be resumed. If more than 4 hours late, then just wait for the next dose. The dose should not be doubled to make up for missed doses.

7.11 Scheduled visits every 30 days +/- 1 week (either in person or by scripted telephone interview with a study coordinator) should include a standardized assessment for recurrent thromboembolism, bleeding episodes, and adverse reactions. Patients should be instructed to report to the clinic immediately (or call 911/go to the Emergency Room) if they had any bleeding, or symptoms of recurrent deep-vein thrombosis, pulmonary embolism, or both. Written patient education materials will be provided to each patient outlining signs and symptoms to watch for regarding VTE recurrences (appendix VI). All suspected episodes of recurrent thrombosis should be investigated with the use of objective imaging.

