- Any malignancy possibly related to cancer treatment (including AML/MDS) should also be reported via the routine reporting mechanisms outlined in each protocol.

10.314 Second Malignancy

- A second malignancy is one unrelated to the treatment of a prior malignancy (and is NOT a metastasis from the initial malignancy). Second malignancies require ONLY routine reporting.

10.315 Pregnancy

If, following initiation of the investigational product, it is subsequently discovered that a study subject is pregnant or may have been pregnant at the time of investigational product exposure, including during at least 5 half-lives after product administration, the investigational product will be permanently discontinued in an appropriate manner (eg, dose tapering if necessary for subject safety).

The site investigator must immediately notify ACCRU of this event via the Pregnancy Surveillance Form (found in the forms packet) within 24 hours and in accordance with SAE reporting procedures in Section 10.4.

Follow-up information regarding the course of the pregnancy, including perinatal and neonatal outcome and, where applicable, offspring information must be reported on a Pregnancy Surveillance Form.

Any pregnancy that occurs in a female partner of a male study participant should be reported to BMS. Information on this pregnancy may also be collected on the Pregnancy Surveillance Form.

Protocol-required procedures for study discontinuation and follow-up must be performed on the subject unless contraindicated by pregnancy

(eg, x-ray studies). Other appropriate pregnancy follow-up procedures should be considered if indicated.

10.316 Overdose

An overdose is defined as the accidental or intentional administration of any dose of a product that is considered both excessive and medically important. All occurrences of overdose must be reported as SAEs.

10.317 Adverse Events of Special Interest

In this study, the following adverse events are to be reported to BMS, regardless of whether these reports are classified as serious or unexpected:

- Potential or suspected cases of liver injury including but not limited to liver test abnormalities, jaundice, hepatitis or cholestasis.
(NOTE: If liver toxicity becomes clinically apparent, it must be evaluated and then reported.)

Adverse drug reactions (related SAEs) should be reported. If hepatic failure, clearly occur due to the meta or primary malignancy, it should not be considered related, therefore not reportable to BMS.

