No formal interim analysis is planned. Risk-benefit will be evaluated by the Mayo Clinic Data Safety and Monitoring Board (DSMB), which will give regular recommendation to the executive committee. Early termination of accrual will be considered if there is evidence of a significant difference in major bleeding rates between the comparators. Access to interim tabular risk benefit data will be restricted.

16.5 Adverse Event Stopping Rule:

The stopping rule specified below is based on the knowledge available at study development. We do note that the Adverse Event Stopping Rule may be adjusted in the event of either (1) the study re-opening to accrual or (2) at any time during the conduct of the trial and in consideration of newly acquired information regarding the adverse event profile of the treatment(s) under investigation. The study team may choose to suspend accrual because of unexpected adverse event profiles that have not crossed the specified rule below.

Accrual will be temporarily suspended to this study if at any time we observe events that the study team considers to be at least possibly related to study treatment (i.e., an adverse event with attribute specified as “possible,” “probable,” or “definite”) that satisfy the following:

- If 5 or more patients in the first 20 treated patients of either of the study arms (or 20% of all patients after 20 are accrued) experience a grade 4 or higher non-hematologic adverse event.

We note that we will review grade 4 and 5 adverse events deemed “unrelated” or “unlikely to be related” to verify their attribution and to monitor the emergence of a previously unrecognized treatment-related adverse event.

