Appendix V
Phone Contact Sheet
Telephone Script

Protocol Title: A Phase III, Controlled, Randomized, Double-Blind Study Evaluating the Safety of Two Doses of Apixaban for Secondary Prevention of Cancer Related Venous Thrombosis in Subjects Who Have Completed at Least Six Months of Anticoagulation Therapy

IRB #:

Principal Investigator: [name]

“Good morning/afternoon. This is _____ calling from [name of institution].

May I speak to _____?”

(If participant is there proceed to the following:)

“I would like to ask you a few questions regarding your blood thinner medication, **apixaban** and the clinical trial in which you have been enrolled. This will allow us to gather very important information about the safety and benefit of using this medication in treating and preventing blood clots.”

“I would like to ask these questions related to our study after confirming your name”

Patient Name _____

1. Over the past month, have you missed any doses of your blood thinner medication?

____ Yes

If yes, approximately how many doses do you estimate that you have missed? _____

If yes, why was the dose missed? _____

____ No, I have not missed any doses of medication

2. Over the past month have you had another blood clot problem?

____ Yes, a DVT (must contact local medical doctor to obtain documentation)

____ Yes, a PE

____ Yes, both a DVT and a PE

____ Yes, something else (e.g. an arterial clot). Please describe: _____

____ No, I have not had any more clots.

3. While you have been taking this medication as recommended have you experienced any major bleeding which required hospitalization or blood transfusion?

____ Yes. Please describe _____

____ No

Any bleeding other than that from an injury? (For example a spontaneous bloody nose.)

____ Yes, Please describe _____

____ No

4. Over the past month, have you undergone any surgeries or invasive procedures?

Yes

If yes, what type of surgery/procedure did you have? _____

What was the date of the procedure? ____-____-____ (MM-DD-YY)

No, I have not had any surgeries or procedures

5. Which of the following best applies to your current activity rating: _____

- A. Fully active, able to carry on all activities before your disease without restriction
- B. Restricted in physically strenuous activity but ambulatory and able to carry out work of a light or sedentary nature, e.g., light house work, office work

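### The Appendix V telephone script lacks the adverse reaction assessment that section 7.11 requires of it, so non-bleeding, non-thrombotic events may be under-ascertained in patients followed by phone

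*Combined protocol and SAP*

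**What the plan says.** Section 7.11 sets the content of the visit held every 30 days, whether in person or by scripted telephone interview: it "should include a standardized assessment for recurrent thromboembolism, bleeding episodes, and adverse reactions".

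In the section 4.0 test schedule, footnote 3 is attached to the monthly column and to the adverse event assessment row. It reads "If it is not feasible for the patient to return to the enrolling center for the monthly reassessment", then "a detailed history will be obtained by phone using a structured interview (see appendix V"). Phone use there depends on feasibility. Inclusion criterion 3.19 has no such condition: follow-up is "either in person at the enrolling institution or by telephone (script in Appendix V"). Section 7.11 likewise offers the two modes as alternatives. No section sets a minimum number of in-person visits.

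The numbered items in Appendix V cover missed doses and the reason, clots (with a write-in option that names an arterial clot), bleeding, surgery or procedures, activity level, weight, new medications, leg swelling, and chest pain or breathlessness. The bleeding item asks "have you experienced any major bleeding which required hospitalization or blood transfusion" and then "Any bleeding other than that from an injury". The closing note tells staff to seek outside records when there is evidence of bleeding or clotting.

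**The concern.** Section 7.11 requires three assessments in the scripted call: thromboembolism, bleeding and adverse reactions. The script delivers the first two and only fragments of the third. Nothing invites the patient to mention any other new or worsened health problem, and an admission for a reason other than major bleeding is never asked about.

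At stake is the completeness of general safety data in a trial whose stated purpose is safety. Section 10.52 wants related grade 2 events and all grade 3 and 4 events regardless of attribution. Section 10.317 names one event of special interest: "Potential or suspected cases of liver injury including but not limited to liver test abnormalities, jaundice, hepatitis or cholestasis". The accrual suspension rule in section 16.5 counts patients who "experience a grade 4 or higher non-hematologic adverse event" judged at least possibly related. All of these depend on the site hearing of the event.

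**Working it through.** The finding rests on comparing sections, not on a calculation.

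**1. Required content against script content.**

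| Required by 7.11 | In Appendix V |
|---|---|
| Recurrent thromboembolism | Yes: clot question with DVT, PE and arterial options; leg swelling; chest pain or breathlessness |
| Bleeding | Yes: major bleeding, then other non-injury bleeding |
| Adverse reactions | Partly: the symptoms above, and indirectly through missed doses, procedures, activity, weight and new medications. No open question, no general hospitalization or emergency visit question |

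**2. How many contacts can be by phone.** Treatment lasts 365 days with contacts every 30 days: 365 / 30 = 12.2, so about 12 monthly contacts. Under 3.19 and 7.11 all of them may be calls. Under footnote 3 they may be calls only when a return is not feasible. The provisions differ, but none caps the number.

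**3. Other scheduled ways to find an event.** In section 4.0, history and exam, CBC, AST or ALT, and creatinine are marked at baseline only. After baseline, a phone-followed patient has no scheduled exam or laboratory test that could reveal an event the call missed. Section 15.19b refers to monitoring liver tests per protocol, but the schedule shows none on treatment.

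**4. Prompts to volunteer information.** Section 7.11 tells patients to report bleeding and symptoms of DVT or PE. Appendix VI is education on DVT and PE. Neither prompts a report of other illness.

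**5. Duties outside the script.** Section 10.51 requires grading of all adverse events at each evaluation, 10.52 lists which go on case report forms, 18.1 schedules monthly Adverse Events (Solicited, Other) forms, and 10.4 requires immediate reporting of serious events. These fix what must be recorded. They do not supply the question that brings an event to light on the phone.

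**6. The section 16.5 rule.** The plan gives thresholds (5 of the first 20 treated in an arm, then 20%) and no operating characteristics, so there is no figure to reproduce. To see only the direction, let p be the true proportion of patients with a qualifying event and c the share recorded. The chance of reaching the first limb is P(X ≥ 5), with X binomial(20, p × c). Both p and c are assumptions; neither is in the documents.

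| p | c = 1 | c = 0.9 | c = 0.75 | c = 0.5 |
|---|---|---|---|---|
| 0.10 | 0.043 | 0.029 | 0.014 | 0.003 |
| 0.25 | 0.585 | 0.480 | 0.316 | 0.095 |

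Under-capture can only make the rule less sensitive. The amount depends entirely on p and c. The p = 0.25 row sits at the threshold itself. Section 15.18 lists major hemorrhage at no more than 3% and nausea and anemia at 3% each. Even at p = 0.10 the first limb is met only about 4% of the time with full capture. The table therefore gives a direction and does not estimate the loss in this trial.

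**The case against.** The strongest reply is that collection does not depend on the script. Sections 10.4, 10.51, 10.52 and 18.1 apply whatever the contact mode, a coordinator may ask more than the script contains, and the Solicited form, which is not in the documents, may prompt for specific terms. Most grade 4 or higher events would be serious and reach the site through serious event reporting. This stands, and it limits the consequence to a risk. It does not remove the mismatch: section 7.11 asks for a standardized assessment, and one that relies on unscripted questions will vary by coordinator and site.

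A reader might go further and infer any of the following. The documents do not support them.

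- **That phone-followed patients' events go uncollected and the section 16.5 count is incomplete.** The duties above still apply, and footnote 3 limits phone use to when a return is not feasible. Only possible under-ascertainment follows.
- **That section 16.5 counts almost nothing the script asks about.** This depends on whether bleeding is classed as hematologic. Section 15.18 groups it that way, but 16.5 does not say. If bleeding counts toward the rule, the leading listed toxicity is asked about directly.
- **That the arterial part of the section 2.31 endpoint is ignored.** The clot question offers an arterial option. No stroke or TIA symptom is asked, so the gap is partial, and section 16.23 analyzes a DVT/PE composite.
- **That the competing events in 16.21 and 16.23 are lost.** An event that ends treatment would surface through the Off Treatment form, and missed doses are asked about with the reason.
- **That the arms are biased.** The trial is double-blind and section 6.21 balances allocation on registering membership. Nothing ties contact mode to dose.

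**Conclusion.** The point holds as an internal inconsistency with a plausible safety cost. Appendix V does not contain the adverse reaction assessment that section 7.11 requires of the scripted call, although footnote 3 lets it replace the visit for that assessment. Non-bleeding, non-thrombotic events may be under-ascertained in phone-followed patients. The most exposed are related grade 2 events, grade 3 events of any attribution, and admissions elsewhere.

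The mismatch itself is certain from the text. The consequence assumes that some sites follow mainly by phone and keep close to the script. Its size, including any loss of sensitivity in section 16.5, cannot be derived from the documents. The primary bleeding comparison is not affected by this gap. The change is worth making because it is cheap and the trial's subject is safety.

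**What to change.** Amend Appendix V as follows.

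- Add an open question on any new or worse health problem since the last contact.
- Add a question on any hospital stay, emergency visit or unscheduled care since the last contact, with the reason.
- Extend the closing note on clinician review and outside records to events found through these two questions.
- State that answers are entered on the Adverse Events (Solicited, Other) and Recurrent Thromboembolism forms already listed in section 18.1.

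Prompts for jaundice and for stroke or TIA symptoms are optional additions; the two questions above are enough to meet section 7.11.

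The cost is a script amendment with IRB review, a few more minutes per call, and more adverse event entries to process. The sample size and the analyses do not change.
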